#### 7.2 Replacement

Data from all enrolled subjects will be reported as outlined in Section 10.3. Specifically, the same subject number will not be re-allotted if a subject withdraws from the study.

#### 8 ASSESMENT OF EFFICACY AND PHARMACOKINETICS

#### 8.1 Description of Efficacy Parameters

Several measures are necessary to complete a thorough

#### 8.1.1 Primary Efficacy Parameter(s)

#### 8.1.1.1 Modified Ashworth Score

The first and best known scale for measuring the degree of spasticity was the Ashworth scale, first developed in 1964 for use in a multiple sclerosis therapeutic trial. Spasticity accounts for much of the disability affecting lower limbs. Modified Ashworth score for the 12 movements of the lower extremities that will be measured will be evaluated as one of the primary efficacy parameters. The Ashworth assessment is the current standard for clinical assessment of lower extremity spasticity and the most commonly used tool to evaluate the efficacy of pharmacologic and rehabilitation interventions for treatment of spasticity.

At each scheduled visit for

Confidential Page 40 of 67

The 6-point modified Ashworth scale scores are presented below:

Score : Degree of Muscle Tone

0 : No increase in tone

1 : Slight increase in muscle tone, manifested by a catch, followed by minimal resistance at the end of the range of movement when the affected part(s) is moved in flexion or extension

Slight increase in muscle tone, manifested by a catch, followed by minimal resistance 1+ : throughout the remainder (less than half) of the range of movement

2 : More marked increase in muscle tone through most of the range of movement, but affected part(s) easily moved

3 : Considerable increase in muscle tone, passive movement difficult

4 : Affected part(s) rigid in flexion or extension

\*note: A change from 1 to 1+ and from 1+ to 2 will each be counted as a 1-point change

	as indicated below:

Confidential Page 41 of 67

#### 8.1.2 Secondary Efficacy Parameter(s)

#### 8.1.2.1 Subject's Global Impression of Severity (SGIS)

Subjects will be asked to rate their overall impression of severity at each of these visits, the subject

#### 8.1.3 Exploratory Parameters

#### 8.1.3.1 Nighttime Awakening and Sleep Time

#### 8.1.3.2 Spasm Frequency

Confidential Page 42 of 67

#### 8.2 Methods and Timing for Assessing and Recording Efficacy Parameters

[figure not shown]
Spasticity will be assessed at every visit using the	. Assessment at Visits 2
through Visit 11 will be performed in the clinic. The subject and his	her caregiver will be instructed
about visit schedules	
. Throu	ghout the study during both the
fixed dose phase (Part 2) and 4-week double blind phase (Part 3)	assessments are to occur

Assessors in the study team (doctors/ physiotherapists/ occupational therapists/ nurses across primary and secondary care) at all sites will be trained on scoring to achieve uniformity in assessments. Attempts will be made to assign the same assessor to an individual study subject for the duration of the study.

Scores for each movement assessed will be recorded in the source documents and entered in the eCRF. Determination of treatment response and derivation of means and averages will be performed at the time of statistical analysis (see Section 10). Statistical analysis of the efficacy parameters will be performed after data-lock according to the statistical analysis plan.

8.3	
8.3.1	
-	
All blood samples will be collected	. The
blood samples will be collected	·

Confidential Page 43 of 67

#### 9 ASSESSMENT OF SAFETY

The Principal Investigator (PI), including the study staff, will monitor the subjects throughout the study period. The staff will be available for subject queries during the regular business hours and *via* an answering service. The PI or qualified medical designee will be on-site and/or available by cell phone throughout the study.

#### 9.1 Description of Safety Parameters

The following safety parameters will be assessed during the study:

- Treatment emergent adverse events
- Daytime sedation
- Vital Signs (seated blood pressure and pulse)
- Clinical laboratory tests
- 12 Lead ECG
- Physical examination
- Neurological evaluation

Confidential Page 44 of 67

#### C-SSRS Suicidality Assessment

#### 9.1.1 Adverse Event

An AE is any untoward medical occurrence during treatment with a pharmaceutical product in a subject that does not necessarily have a relationship with the treatment being administered. An AE can therefore be any unfavorable and unintended sign (including an abnormal laboratory finding), symptom, or disease temporally associated with the use of a medicinal (investigational) product, whether or not related to the medicinal (investigational) product.

Untoward medical experience occurring during medication-free pre-treatment periods does not meet the above-mentioned definition of an AE. Nevertheless, they have to be documented in the same way as AE. Each subject will be queried generally for the occurrence of adverse experiences prior to study drug administration and throughout the subject"s participation in the study. During and following a subject's participation in this study, the Investigator has to ensure that adequate medical care is provided to a subject for any AE, including clinically significant laboratory values, related to the study. The subject will be treated and/or followed up until the symptom(s) returns to normal or stabilizes, as judged by the PI.

#### 9.1.2 Serious Adverse Event

A SAE or serious adverse drug reaction is any untoward medical occurrence that, at any dose:

- Results in death
- Is life-threatening
- Requires in-patient hospitalization or prolongation of existing hospitalization
- Results in persistent or significant disability/incapacity

Or

• Is a congenital anomaly/birth defect

NOTE: The term "life-threatening" in the definition of "serious" refers to an event in which the subject was at risk of death at the time of the event; it does not refer to an event, which, hypothetically, might have caused death if it were more severe.

Medical and scientific judgment should be exercised in deciding whether expedited reporting is appropriate in other situations, such as important medical events that may not be immediately life-threatening or result in death or hospitalization, but may jeopardize the subject or may require intervention to prevent one of the other outcomes listed in the definition above. These should usually also be considered serious.

Examples of such events are intensive treatment in an emergency room or at home for allergic bronchospasm; blood dyscrasias or convulsions that do not result in hospitalization; or development of drug dependency or drug abuse.

Confidential Page 45 of 67

#### 9.1.3 Pregnancy

A urine pregnancy test will be performed at screening and subjects with a positive test will be excluded from study. Women of child-bearing potential will be instructed to practice an acceptable method of birth control for the duration of the study. A follow-up urine pregnancy screen will be conducted at Visit 7. However, if subject becomes pregnant during the study, the pregnancy will be recorded as a significant medical event and procedure for expedited reporting (Section 9.2.1) will be followed. The pregnancy will be followed until its outcome, and the outcome will be reported as a significant medical event and procedure for expedited reporting (Section 9.2.1) will be followed.

### 9.2 Methods and Timing for Assessing, Recording, and Analyzing Safety Parameters

#### 9.2.1 Eliciting, Documentation and Reporting of Adverse Events and Intercurrent Illnesses

Information on AEs will be derived by questioning the subjects in general terms (e.g., "How do you feel?" or "How have you been feeling since the last questioning?" respectively), by subjects' spontaneous reports, or by observation.

AEs will be documented on the source document. The AE will be entered to the AE eCRF-pages. The following information will be given for each AE: description of the AE, start date, stop date, severity, pattern (continuous/intermittent), action taken, outcome, seriousness, and causality assessment.

Confidential Page 46 of 67

#### 9.2.1.1 Rating of Adverse Events

The following system will be used to assess causality as well as intensity of the AEs.

TERM	DEFINITION*	d to assess causality as well as intensity of the AEs.  CLARIFICATION
Unrelated	Those adverse events who environment, etc.)	ich, after careful consideration, are clearly due to extraneous causes (disease,
Unlikely	A clinical event, including laboratory test abnormality, with a temporal relationship to drug administration which makes a causal relationship improbable, and in which other drugs, chemicals or underlying disease provide plausible explanations.	It does not follow a reasonable temporal sequence (Improbable temporal relationship) from administration of the drug.      It could also be explained by patient's concurrent disease, environmental factors, medical history and other concomitant drugs or chemicals including food-drug interactions
Possibly	A clinical event, including laboratory test abnormality, with a reasonable time sequence to administration of the drug, but which could also be explained by concurrent disease or other drugs or chemicals. Information on drug withdrawal may be lacking or unclear.	It follows a reasonable temporal sequence from administration of the drug.      It could also be explained by patient's concurrent disease, environmental factors, medical history and other concomitant drugs or chemicals (including food-drug interactions).      There is no information or uncertainty with regard to what has happened after stopping the drug.
Probably	A clinical event, including laboratory test abnormality, with a reasonable time sequence to administration of the drug, unlikely to be attributed to concurrent disease or other drugs or chemicals, and which follows a clinically reasonable response on withdrawal (dechallenge). Rechallenge information is not required to fulfil this definition.	
 
It follows a reasonable temporal sequence from administration of the drug.
 
It could not be readily explained (unlikely) by the patient's concurrent disease, environmental factors, medical history and other concomitant drugs or chemicals including food-drug interactions.
 
It disappears or decreases in severity on cessation or reduction in dose or on administration of a specific antagonist wherever possible. There are important exceptions when an adverse event does not disappear upon discontinuation of the drug, yet drug relatedness clearly exists.
 
No rechallenge information is available or possible.
 

Certain	A clinical event, including laboratory test abnormality,	I. It follows a plausible time sequence to drug intake ,this means that there is a positive argument in sufficient detail to support the view that the drug

Confidential Page 47 of 67

TERM	DEFINITION*	CLARIFICATION
	occurring in a plausible time relationship to drug administration, and which cannot be explained by concurrent disease or other drugs or chemicals. The response to withdrawal of the drug (dechallenge) should be clinically plausible. The event must be definitive pharmacologically or phenomenologically, using a satisfactory rechallenge procedure if necessary.	is causally involved, pharmacologically or pathologically e.g. pharmacokinetics and type of reaction.  2. It could not be explained by patient's concurrent disease, environmental factors, medical history and other concomitant drugs or chemicals including food-drug interactions (i.e. no alternative causes).  3. It disappears or decreases in severity on cessation or reduction in dose or on administration of a specific antagonist wherever possible.  4. It is an objective and specific medical disorder or a recognized pharmacological phenomenon for instance ,grey baby syndrome" and chloramphenicol or anaphylaxis immediately after the administration of a drug that had been given previously. This means that any other event is automatically excluded and can never qualify for 'Certain' (even in the case of a positive rechallenge observation).  5. It reappears on readministration of the drug (only if ethically correct i.e. in case of non-serious, and easily treatable adverse events).
• *http:/	//www.who-umc.org/Graphi	ics/24734.pdf (as accessed on 19-Nov-2011).

The severity of an adverse event is characterized as:

- Mild: AE which is easily tolerated
- Moderate: AE sufficiently discomforting to interfere with daily activity.
- Severe: AE, which prevents normal daily activities.

#### 9.2.1.2 Documentation and Reporting of Immediately Reportable Adverse Events

Subject will be examined for any new medical conditions or worsening of the pre-existing ones. Any change in pre-existing conditions or new conditions must be entered on the AE page of the eCRF and any medication given on the concomitant medication pages.

Any unexpected AE that could adversely affect the safety of the subjects or the conduct of the study and any SAE, which occurs during the course of this study, will be reported to the pharmacovigilance department of the CRO within 24 hours of the Investigator becoming aware of the event. Any new information relating to an SAE that subsequently becomes available should also be faxed to the CRO Drug Safety within 24 hours of the Investigator becoming aware of the information.

[figure not shown]
All SAEs must be reported, whether or not considered attributable to the study drug on a separate SAE Report Form according to the following procedures:

As much information as possible should be supplied at the time of the initial report with at least the following information:

Name, address, and telephone number of the reporting Investigator

Confidential Page 48 of 67

- Investigational product(s)
- Protocol number
- Subject identification number, initials, sex and date of birth
- Description of the AE, reason considered serious, measures taken and outcome (if resolved)
- Likelihood of drug causation of the adverse event assessed by the Investigator.

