	For the primary efficacy analysis, subjects who provide modified Ashworth and CGIC scores at Visit 11 and meet the treatment failure criterion at Visit 11, or who have met the treatment failure criterion at any prior visit will be classified as being treatment failures. All other subjects will be classified as not being treatment failures.
Secondary Efficacy Outcomes:	Subject Global Impression of Severity (SGIS)
Safety Assessments:	
 
Treatment Emergent Adverse Events
 
Daytime sedation
 
Vital Signs (seated blood pressure and pulse)
 
Clinical laboratory tests
 
12 Lead ECG
 
Physical examination and neurological evaluation
 
Columbia – Suicide Severity Rating Scale
 

Treatments:	•
Study Population:	Subjects aged 18 years and above with spasticity due to multiple sclerosis with acceptable symptom control
Number of Subjects:	Approximately 300 subjects will be enrolled to ensure that at least 240 subjects are randomized at the beginning of
Number of Centers:	Up to 35 centers
Setting:	Out-patient clinics
Statistical Methods:	Efficacy Analyses: The primary efficacy analysis will be performed on an intent-to-treat (ITT) population, defined as all subjects who were randomized to double-blind study drug at Visit 7 and subsequently received at least one dose of study medication.
	).
	A per protocol (PP) population may also be analyzed (if it differs from the ITT population overall by more than 10% in sample size), defined as all ITT population subjects who had at least one on-treatment assessment in Part 3, and did not have any major protocol violation (such as poor compliance).

Confidential Page 3 of 67

Confidential Page 4 of 67

used medications.

Subject listings will be provided for all safety parameters as well as recently and concurrently

Table 1: STUDY DESIGN AND SCHEDULE OF ASSESSMENTS

		1 a	DIC 1. 510	DESIGN I	ALID SCHED	ULE OF ASS	ESSIVIE VIS					
Visit	S	Run- In		Open-La	abel				Double-		bo-Controlle ation	d Down-
	Screening											
	(-14 days)	Visit 1	Visit 2	Visit 3	Visit 4	Visit 5	Visit 6	Visit 7	Visit 8	Visit 9	Visit 10	Visit 11
Week												
Informed consent	×		_			_						
Demographics	×											
Medical and medication	×	×										
history												
Physical examination 	×											× 
Neurological examination	×											× 
Vital sign measurements 	×	×	×	×	×	×	×	×	×	×	×	×
		x										

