#### 10.4.5.1 Adverse Events

All treatment-emergent adverse events (TEAE) will be coded in a standardized manner for regulatory activities. TEAEs will be coded according to body systems and preferred terms. A

Confidential Page 59 of 67

 
TEAE is defined as any event that only occurred after administration or that existed before drug administration but increased in severity or treatment attribution. For the randomized withdrawal phase, emergent events will be determined relative to the double-blind medication.
Adverse events reported as pre-existing at the start of the run-in or that emerge during the treatment phase will be considered pre-treatment adverse events. These will be summarized separately.
The incidence of TEAEs and SAEs will be summarized for the s (Part 2) and also by treatment group during the double-blind, par (Part 3). For each part, the incidence of TEAEs will be presented by system organ classification and preferred terms according to the Medical Dictionary for Regulatory Activities (MedDRA®), by causality, by severity, and by action taken. In addition, separate summaries will be prepared with subjects categorized by sex, age (below 65 years of age and 65 years of age and older), and race.
The effects of concomitant medications and/or medical conditions present at screening will also be explored. Should any medications be used by or conditions be present in 20% or more of the subjects overall, subjects will be categorized accordingly and the incidence of TEAEs in each par summarized. Additional drugs or diagnoses of interest may be identified during the blinded data review.
In addition, adverse events will be listed for all subjects, including verbatim and coded terms.
10.4.5.2

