#### 6.2.1.3 Derivation of Primary Endpoint

The primary efficacy variable is the proportion of subjects who become a Treatment Failure during the double-blind randomized withdrawal part (Part 3). Using the primary efficacy variable, the CRO will perform a determination of failures (the blinded failure analysis). A subject's response status will be determined after database lock, but prior to unblinding the data. A subject who meets the following criterion will be considered a treatment failure:

• A CGIC of ≥ 5 ("minimally worse" to "very much worse") and at least one movement with a ≥ 1 unit increase in MAS from Baseline (A change from 1 to 1+ and 1+ to 2 will be counted as a 1-unit change)

The MAS at a given visit will be	e recorded for each of the	12 movements measured.	

For the Treatment Failure analysis, subjects who provide MAS and CGIC scores at Visit 11 and meet the treatment failure criterion at Visit 11,

21Sep2017

All other subjects will be classified as not being Treatment Failures.

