#### **Subgroup Analyses** 6.2.4.6

## **6.3 Safety Analysis**

#### 6.3.1 Adverse Events

All adverse events will be coded using version 15.0 of MedDRA, which will be noted in the CSR.

Adverse events reported as pre-existing at the start of the run-in emerge during the treatment phase will be considered pre-treatment adverse events; these will be flagged in a listing.

A treatment-emergent adverse experience (TEAE) is defined as any event that only occurred after administration or that existed before drug administration but increased in severity or treatment attribution.

The duration of an AE will be calculated as:

$$Duration = (AE End Date - AE Onset Date) + 1$$

When AE start and/or stop dates are missing, the following imputations will be made (subject to medical review):

- Missing AE Start Dates
- 1. If onset date is completely missing, then onset date is set to date of first dose
- 2. If year is present and (month and day are missing), or (month is missing but day is present):
  - a. If year = year of first dose, then set date to first dose date
  - b. If year < year of first dose and medication stop month and year are available, then set to first of the end month
  - c. Otherwise if year < year of first dose, then set month and day to December 31st.
  - d. If year > year of first dose, then set month and day to January 1st.
- 3. If month and year are present and day is missing:
  - a. If year=year of first dose and

- i. If month = month of first dose then set day to day of first dose date
- ii. If month < month of first dose then set day to last day of month
- iii. If month > month of first dose then set day to first day of month
- b. If year < year of first dose then set day to last day of month
- c. If year > year of first dose then set day to first day of month
- 4. If the AE start date is completely missing and the corresponding stop date is completely missing, the AE start date will remain missing.

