	Incidence of Treatment-Emergent Adverse Events by Descending Order of Frequency
Table 14.3.1.1.3	of Preferred Terms in Part 2 (Safety Population)
Table 14.3.1.1.4	Incidence of Treatment-Emergent Adverse Events by Maximum Severity in Part 2 (Safety Population)
14010 14.5.1.1.4	Incidence of Treatment-Emergent Adverse Events by Highest Relationship in Part 2
Table 14.3.1.1.5	(Safety Population)
	Incidence of Treatment-Related Treatment-Emergent Adverse Events by Highest
Table 14.3.1.1.6	Relationship in Part 2 (Safety Population)
Table 14.3.1.1.7	Incidence of Treatment-Emergent Adverse Events Leading to Discontinuation in Part 2 (Safety Population)
14016 14.5.1.1./	Incidence of Treatment-Emergent Adverse Events by Gender in Part 2 (Safety
Table 14.3.1.1.8	Population)
Table 14.3.1.1.9	Incidence of Treatment-Emergent Adverse Events by Age Group in Part 2 (Safety
	Population)
Table 14.3.1.1.10	Incidence of Treatment-Emergent Adverse Events by Race in Part 2 (Safety
Table 14.3.1.1.11	Population) Incidence of Treatment-Emergent Adverse Events by Concomitant Medications in at
14010 14.5.1.1111	Least 20% of Subjects in Part 2 (Safety Population)
Table 14.3.1.1.12	Incidence of Treatment-Emergent Adverse Events by Medical Conditions Present in
	at Least 20% of Subjects at Screening in Part 2 (Safety Population)
Table 14.3.1.1.13	Incidence of Treatment-Emergent Adverse Events by Renal Function in Part 2 (Safety
	Population) Incidence of Treatment-Emergent Adverse Events by Dose at Earliest Onset in Part 2
Table 14.3.1.1.14	(Safety Population)
Table 14.3.1.2.1	Overview of Adverse Events by Treatment Group in Part 3 (Safety Population)
14010 1 1.0.1.2.1	Incidence of Treatment-Emergent Adverse Events by Treatment Group in Part 3
Table 14.3.1.2.2	(Safety Population)
	Incidence of Treatment-Emergent Adverse Events by Descending Order of Frequency
Table 14.3.1.2.3	of Preferred Terms by Treatment Group in Part 3 (Safety Population)
	Incidence of Treatment-Emergent Adverse Events by Maximum Severity by
Table 14.3.1.2.4	Treatment Group in Part 3 (Safety Population)

	Incidence of Treatment-Emergent Adverse Events by Highest Relationship by	
Table 14.3.1.2.5	Treatment Group in Part 3 (Safety Population)	
Table 14.3.1.2.6	Incidence of Treatment-Related Treatment-Emergent Adverse Events by Highest Relationship by Treatment Group in Part 3 (Safety Population)	

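### Recorded worsening of spasticity falls into the Part 3 by-arm TEAE totals with no planned split, so the totals can dilute a true excess of other events on continued drug

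*Protocol*

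**What the plan says.** **Recording rule.** Protocol 9.2.1.2 has an active part, "Subject will be examined for any new medical conditions or worsening of the pre-existing ones", and an entry duty, "Any change in pre-existing conditions or new conditions must be entered on the AE page of the eCRF". Neither sentence names spasticity, and neither exempts it.

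**Population.** The synopsis defines the study population as "Subjects aged 18 years and above with spasticity due to multiple sclerosis with acceptable symptom control", so spasticity is a pre-existing condition in every subject.

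**TEAE definition.** Protocol 10.4.5.1 counts an event "that existed before drug administration but increased in severity or treatment attribution". SAP 6.3.1 uses the same words. The protocol adds: "For the randomized withdrawal phase, emergent events will be determined relative to the double-blind medication". The readable SAP text does not repeat that sentence, but nothing in it contradicts it.

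**Efficacy failure.** SAP 6.2.1.3 requires a CGIC of 5 or more together with "at least one movement with a ≥ 1 unit increase in MAS from Baseline". This is a worsening of the same pre-existing condition.

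**Outputs.** SAP 6.3.1 plans an overall summary that includes subjects with at least one TEAE and breakdowns by highest severity, relationship and action taken. SAP 9.1 lists the Part 3 versions by treatment group:
- overview: Table 14.3.1.2.1
- maximum severity: Table 14.3.1.2.4
- treatment-related: Table 14.3.1.2.6
- leading to discontinuation: Table 14.3.1.2.7

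By-arm tables by system organ class and preferred term are also listed. No listed table shows TEAEs with and without spasticity worsening.

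**Where the split does exist.** SAP 6.1.1 treats loss of efficacy or clinical worsening as a discontinuation reason distinct from an adverse event. The adverse event tables have no matching separation.

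**The concern.** Determining the safety profile against down-titration to placebo is one of the primary objectives (SAP 3.1.1). In a randomized withdrawal design the placebo arm is expected to lose symptom control. If that loss is recorded on the adverse event page, part of the efficacy result is counted again as a safety event, mainly on placebo.

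The effect has a direction. The better the drug works, the more the placebo total rises, and the smaller any excess of other events on continued drug looks in the aggregate rows. A study report is likely to quote those rows. The size depends on how often sites enter worsening spasticity as an adverse event, and no readable text settles that.

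**Working it through.** There is no stated figure to reproduce. The readable documents give no failure rate, TEAE rate or power for this comparison, so every rate below is an assumption chosen to show the range.

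**Inputs (assumed)**
- *a* = proportion with at least one TEAE other than spasticity worsening: 30% drug, 20% placebo, a true difference of +10 points.
- *f* = treatment failure proportion: 20% drug, 40% placebo.
- *q* = share of failures entered as adverse events, the same in both arms.
- Within each arm, other TEAEs and failure are independent.

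**Formula.** Any TEAE in an arm = 1 - (1 - a)(1 - f·q).

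| q | Drug | Placebo | Difference |
|---|---|---|---|
| 0.25 | 1 - 0.70 × 0.95 = 33.5% | 1 - 0.80 × 0.90 = 28.0% | +5.5 points |
| 0.50 | 1 - 0.70 × 0.90 = 37.0% | 1 - 0.80 × 0.80 = 36.0% | +1.0 point |
| 1.00 | 1 - 0.70 × 0.80 = 44.0% | 1 - 0.80 × 0.60 = 52.0% | -8.0 points |

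**When does the sign change?** Setting the two arms equal gives q* = (a_drug - a_placebo) / [(1 - a_placebo)·f_placebo - (1 - a_drug)·f_drug]. A q* above 1 means that reversal is impossible.

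| Other TEAEs (drug, placebo) | Failure (drug, placebo) | q* | Difference if all entered |
|---|---|---|---|
| 30%, 20% | 20%, 40% | 0.10 / (0.32 - 0.14) = 0.56 | -8 points |
| 30%, 20% | 20%, 50% | 0.10 / (0.40 - 0.14) = 0.38 | -16 points |
| 30%, 20% | 10%, 20% | 0.10 / (0.16 - 0.07) = 1.11, none | +1 point |
| 30%, 20% | 10%, 15% | 0.10 / (0.12 - 0.07) = 2.0, none | +5 points |
| 40%, 25% | 20%, 40% | 0.15 / (0.30 - 0.12) = 0.83 | -3 points (true +15) |
| 25%, 20% | 20%, 40% | 0.05 / (0.32 - 0.15) = 0.29 | -12 points (true +5) |

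The difference shrinks in every scenario. Reversal needs a sizeable efficacy effect and a substantial share of failures entered.

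**Can the preferred-term tables repair the total?** Not from the counts alone, because one subject can have both kinds of event. Take the all-entered row. On placebo, any TEAE is 52% and the spasticity term is 40%. From those two figures the rate of other TEAEs could lie anywhere between 52 - 40 = 12% and 52%. On drug, 44% and 20% leave a range from 24% to 44%. The assumed 20% and 30% lie inside these ranges but cannot be recovered from them. Rates for the other terms would narrow the ranges without fixing the answer. Subject-level data are needed.

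**The case against.** **The rule is generic.** Protocol 9.2.1.2 never names the disease under study, and elsewhere the documents keep lost efficacy apart from adverse events: SAP 6.1.1 does so for discontinuation reasons, and Protocol 5.3 lists intolerable spasticity separately from a treatment-related serious event. This stands as a reason why sites might not enter it. It is not an exemption, and it leaves practice open to vary between sites.

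**Failure is not the same as a TEAE.** A reader might infer that every subject who meets the failure criterion has a TEAE by the plan's own rules. The documents do not support that. Failure is derived after database lock from CGIC and Ashworth scores, whereas adverse events come from general questioning, spontaneous report or observation (Protocol 9.2.1). A one-unit rise in one of 12 movements need not become a recorded event. This stands, and it is why *q* is left open.

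**The inputs are invented.** This also stands. A 10-point excess of new events on drug may be generous, because subjects have already spent 12 to 16 weeks on a fixed dose and unchanged side effects are not emergent in Part 3. A smaller true excess, however, is reversed more easily: at 25% and 20% the threshold falls to about 29%.

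**The term is visible by arm.** It would appear in the preferred-term tables, and the separate loss-of-efficacy reason should limit the effect on the discontinuation table. Both points stand, but they do not restore the any-TEAE comparison.

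**Worsening after withdrawal is a genuine untoward event.** Removing it from the headline would replace one selective total with another. This is accepted, and the fix keeps the full total.

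**Redaction.** The adverse event sections have gaps, and an exemption in the hidden text cannot be excluded.

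**Conclusion.** The point holds as one about aggregate tables. On the readable text, recorded worsening of spasticity is a Part 3 TEAE, and no planned output separates it. The any-TEAE and highest-severity rows can therefore dilute a true excess of other events on continued drug. The treatment-related and discontinuation rows can too, depending on investigator coding.

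Under the base assumptions, +10 points becomes +5.5, +1 or -8 as the share entered goes from a quarter to a half to all. Reversal needs more than about 56% entered. With failure of 10% and 15% the difference is at most halved, to +5.

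A reader might infer that the by-arm safety comparison will be reversed, or that the by-term results are also distorted. Neither follows. Reversal depends on assumed rates and an unknown share entered, and rows for other preferred terms are unaffected. The readable safety text plans descriptive adverse event summaries, so no formal test is biased. This is a worthwhile, inexpensive improvement and does not indicate a defect in the primary analysis.

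**What to change.** In SAP 6.3.1, add a paragraph that fixes, before unblinding, a short list of preferred terms denoting return or worsening of spasticity. The blinded review in SAP 5.5 already examines adverse events and is the natural place to agree the list. Produce Tables 14.3.1.2.1, 14.3.1.2.4, 14.3.1.2.6 and 14.3.1.2.7 both with and without those terms. Report the two versions side by side in the between-arm safety statement, keeping the all-TEAE total. If redacted text already holds an exemption, one sentence in SAP 6.3.1 confirming it would answer the point.

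The cost is one SAP paragraph, an agreed term list, four repeat tables and two sets of totals to explain. Data collection, subject management and the primary efficacy analysis do not change.
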